4. SAMPLE SIZE AND POWER CONSIDERATIONS

The sample size is driven by interest in the IOP lowering effect of H-1337. The study is designed to test whether one or more concentrations of H-1337 are superior to the vehicle control in the reduction of IOP. With $n = 20/\text{group}$ this protocol is powered at 94% to detect a difference in IOP reduction of 4.0 mmHg between groups against a standard deviation of 3.5 mmHg (2-sided t-test, $\alpha=0.05$).

Adverse events: With 20 subjects per group there is a 95% certainty that an event that is not observed would have a true incidence rate of no more than 15%.

Hyperemia: Scored on a 5-point scale from 0 to 3. Assume the SD is 20% of the scale range or 1 unit. Then, with $n = 20/\text{group}$ there is 86% power to detect a mean difference of 1 unit between pairs of groups (2 group two-sided t-test, $\alpha=0.05$). If a response is defined as a hyperemia score ≥ 3 and the response rate in the control group is 10%, then with $n = 20/\text{group}$ there is 85% power to detect a difference in response rates of 46% (Fisher's exact test).

In general, with 20 subjects per group there is 86% power to detect an effect size of 1.0.

If a concentration is chosen that is less than the maximum, the safety data from the higher doses can be combined to increase power.

5. ANALYSIS POPULATIONS

The Safety Population will include all randomized subjects who receive at least one dose of study medication.

All subjects who receive study medication and who complete at least one on-therapy study visit will comprise the Intent to Treat Population.

Subjects who receive study medication, satisfy pre-randomization inclusion/exclusion criteria, and who complete at least one on-therapy study visit will be evaluable for a Per Protocol Population analysis. Individual subject visits and data points that do not satisfy protocol criteria may be excluded from per protocol analyses. Evaluability will be determined prior to breaking the code for masked treatment assignment.

All analyses will be based on the actual treatment each subject received.

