6 ASSESSMENT OF EFFICACY

6.1 Efficacy Parameters

Primary Efficacy Endpoints:

The primary efficacy measure will be the mean change in IOP from Baseline (Day 0) IOP (mmHg) for each group on Days 14 and 28 at each matched time point as compared to vehicle. IOP will be measured according to the Schedule of Assessments and Procedures Table.

Secondary efficacy endpoints:

1. The observed IOP, mean change from Baseline, and % change from Baseline IOP at each matched time point at each visit, and
2. The mean observed, mean change from Baseline and mean % change from Baseline for the mean diurnal IOP at each visit, and
3. The proportion of subjects reaching a target IOP (≤ 18 mmHg) at each time point and with the mean diurnal IOP for each visit. Each concentration will be compared to vehicle and the difference in means between treatment arms will be presented.

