8.3 Subject Population(s) for Analysis

Up to approximately 4 to 8 US sites will be active.

All subjects who receive IP and at least one dose will be evaluable for the safety analysis. For efficacy considerations, the primary analysis population will be the intent-to-treat (ITT) population. All subjects who receive study medication and who complete at least one on-therapy study visit will be evaluable for the ITT analyses. Subjects who receive study

medication, satisfy pre-randomization inclusion/exclusion criteria, and who complete at least one on-therapy study visit will be evaluable for a per protocol population analysis. Individual subject visits and data points that do not satisfy protocol criteria may be excluded from per protocol analyses. Evaluability will be determined prior to breaking the code for masked treatment assignment.

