2.5 Study Treatments

Subjects will receive one of four dosing arms: H-1337 at concentrations of 0.06%, 0.2%, or 0.6%, or a control vehicle. IP will be administered BID unilaterally in the study eye for the first 3 days, then BID OU from Day 4 to Day 28.

The IWRS will assign a number to subjects who qualify for randomization. The first IP bottle will be dispensed on Day 0 (Baseline) and the second IP bottle will be dispensed to the subject on Day 14. The third IP bottle will serve as a back-up if the subject needs a replacement IP bottle.

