7.1 Subject Disposition

Subject disposition, including the number of subjects randomized, treated, and completing the study (and completing each study visit), will be tabulated by treatment group. The percentage of subjects treated and completing the study will be based on the total number randomized.

Eligibility criteria exemptions and major protocol deviations will be summarized by treatment group and presented in a listing. Major protocol deviations may include the following: violation of inclusion or exclusion criteria, using prohibited medications, non-adherence to study treatment schedule.

The total number and percentage of subjects included in each of the analysis datasets described in Section 5 will be summarized by treatment group, with percentages based on the total number randomized subjects.

Discontinuations and the reasons for discontinuation will be summarized for all randomized subjects. Summaries will include the number and percentage of subjects within each treatment group. Reasons for discontinuation following the receipt of study drug will include the following:

1. Protocol violation
2. Lost to follow-up
3. Adverse event
4. Non-compliance
5. Subject withdrew consent
6. Investigator decision
7. Uncontrolled IOP
8. Other

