7.2 Demographic and Baseline Characteristics

The demographic and baseline characteristics will be summarized for all randomized subjects by treatment group.

Continuous variables such as age will be summarized using descriptive statistics (n, mean, standard deviation, median, minimum, and maximum), and categorical variables such as gender, race, and ethnicity will be summarized using counts and percentages of subjects.

Age will be determined as the whole integer number of years from the date of birth (DOB) to the date of the screening visit, i.e., the truncated integer difference between the DOB and Visit 1.

Baseline comparability between treatment groups will be assessed via descriptive statistics.

Prior medications will be tabulated by preferred term (WHO drug dictionary).

Medical and surgical history classified using MedDRA dictionary will be presented in a listing.

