7.4 Intraocular pressure

The comparisons among treatment groups in IOP will be done for the various endpoints and time points. The outline of the analyses and groups is presented in Appendix 2.

For each visit in which IOP is measured descriptive statistics at each time point will be presented for the observed, change from baseline and % change from baseline values. In addition, at visits where five assessments are made descriptive statistics will be presented for the average of the observed values and the change from baseline and percent change from baseline where the values will be computed using average of five corresponding values at Day 0 as a baseline.

Descriptive statistics of IOP measures described above will be presented for the study eye, non-study eye and average of both eyes by time point and treatment group.

The 95% confidence intervals of the mean IOP by treatment group and time point and for diurnal IOP as well as for corresponding change from baseline will be presented.

For the IOP, diurnal IOP, and their change from baseline, each of the active treatment groups will be compared to the placebo group using the analysis of covariance (ANCOVA) model, separately for each time point. Baseline value will be used as a covariate. The difference between treatment groups in adjusted least-square means will be presented. Mean diurnal IOP will be presented as the mean of all values (including the 8 pm IOP value) (12-hour diurnal) and mean of all values up to the 4 pm IOP value (8 hour diurnal). If a subject is missing any time point for the calculation of the diurnal IOP, that subject will be excluded from the affected diurnal IOP analysis in the per protocol population.

The proportion of subjects reaching a target IOP (≤ 18 mmHg) at each time point and with the mean diurnal IOP for each visit will be presented by treatment group.

Within each dose level the change from baseline IOP will also be compared (a within subject comparison) with descriptive statistics.

Exploratory summaries may be presented to examine if treatment effects differ depending on iris color, age and baseline IOP.

Each comparison will be tested at the significance level of 0.05. No adjustments for multiple comparisons will be made.

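### SAP section 5 groups every analysis by treatment received, so the ITT comparison of IOP with vehicle is as-treated as written

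*SAP*

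**What the plan says.** Protocol section 8.3 sets the efficacy population: "For efficacy considerations, the primary analysis population will be the intent-to-treat (ITT) population". Protocol section 6.1 defines the primary efficacy measure as mean change in IOP from Day 0, "for each group on Days 14 and 28 at each matched time point as compared to vehicle".

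SAP section 5 defines the set: "All subjects who receive study medication and who complete at least one on-therapy study visit will comprise the Intent to Treat Population". This says who is in the set, not which arm each subject is counted in. The section then ends with a rule on grouping: "All analyses will be based on the actual treatment each subject received".

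SAP section 7.4 gives the test: "each of the active treatment groups will be compared to the placebo group using the analysis of covariance (ANCOVA) model". Appendix 2 of the SAP lists the comparison only as H-1337 against vehicle. Neither place mentions the randomised arm.

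Two descriptive sections cover everyone randomised. SAP section 7.1 says "The percentage of subjects treated and completing the study will be based on the total number randomized", and SAP section 7.2 says "The demographic and baseline characteristics will be summarized for all randomized subjects by treatment group".

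**The concern.** An ITT comparison normally means that subjects are counted in the arm to which they were randomised. That is what ties the test to the randomisation, which here is stratified by baseline IOP. The SAP keeps the ITT label but attaches a rule that would move a subject to another arm in the efficacy tests after a dispensing error. A programmer who follows section 5 literally would group the ITT tables by treatment received, while a reader of the study report would take the label to mean the opposite.

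This matters because both documents say that interest in IOP lowering drives the sample size and that the study is designed to test superiority over vehicle. Grouping by treatment received is suitable for the safety analyses, which serve the primary objective. Only the efficacy grouping, and the tables that cover all randomised subjects, are in question.

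**Working it through.** **Step 1. Is there an exception?** Five places could contain one.

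| Place | What it settles | Grouping by randomised arm? |
|---|---|---|
| Protocol 8.3 | ITT is the primary efficacy population; membership | Not stated |
| Protocol 6.1 | Measure, visits, comparison with vehicle | Not stated |
| SAP 5 | Membership of all three sets, then the grouping rule | No: treatment received, all analyses |
| SAP 7.4 | ANCOVA, each active group against placebo | Not stated |
| SAP Appendix 2 | Endpoints, time points, comparison | Not stated |

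The only grouping rule in either document is the one in SAP 5, so it governs the ITT analysis.

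**Step 2. Reproduce the planned power.** Inputs from SAP section 4 and protocol section 8.1: n = 20 per group, difference 4.0 mmHg, SD 3.5 mmHg, two-sided alpha 0.05, t-test.

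- Noncentrality = 4.0 / (3.5 × √(1/20 + 1/20)) = 4.0 / 1.107 = 3.61.
- With 38 degrees of freedom the critical t is 2.024, and power is 94.1%. The documents state 94%.

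**Step 3. What the grouping changes.** With no error, received and randomised treatment coincide, and both groupings give 94.1%. The documents give no error rate, so the following is illustration only. Suppose m of the 20 subjects in one active arm receive vehicle throughout and respond as vehicle subjects do.

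*As-treated.* The arms become 20 − m and 20 + m, and the difference stays at 4.0 mmHg.
- m = 1 (19 and 21): noncentrality 3.61, power 94.0%.
- m = 2 (18 and 22): noncentrality 3.60, power 93.9%.

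*As-randomised.* The arms stay at 20 and 20. The expected difference is 4.0 × (1 − m/20). The active-arm variance is 3.5² + 4.0² × (m/20)(1 − m/20), and it is averaged with the vehicle variance of 12.25.
- m = 1: difference 3.8; active variance 12.25 + 0.76 = 13.01; pooled SD √12.63 = 3.55; noncentrality 3.38; power 90.9%.
- m = 2: difference 3.6; active variance 12.25 + 1.44 = 13.69; pooled SD √12.97 = 3.60; noncentrality 3.16; power 86.9%.

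The mixture is not exactly normal, so the as-randomised figures were checked by simulation (200,000 trials each). Simulated power was 94.1% with no error, 91.3% for m = 1 and 87.4% for m = 2.

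All of these figures are for the t-test used in the sample-size section. The ANCOVA would have its own power, which depends on a baseline correlation that the documents do not give.

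**The case against.** The strongest reply is that nothing is shown to go wrong. As-treated analysis is dangerous mainly when patients or physicians choose the treatment for reasons linked to outcome. Here an interactive web system assigns treatment, the bottles are identical, investigators are masked and no crossover is planned. A subject would get another arm's treatment only through a handling error, and the documents suggest no route by which outcome could drive one. The power figures even favour the current text. Efficacy is a secondary objective, the protocol calls the trial small and exploratory, and the ITT set already requires dosing and an on-therapy visit.

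Most of this stands. It lowers the likely size of the problem, and the power cost of the fix is real. It does not supply the missing exception. The protocol chose ITT for efficacy, and the SAP attaches a rule that departs from it. Power gained by moving subjects between arms is no reason to give up the randomised grouping in the main efficacy test.

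Three stronger readings are tempting, and the documents do not support them.

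- A reader might infer that the SAP contradicts the protocol. Protocol section 8.3 does not state how subjects are grouped, so there is no direct contradiction.
- A reader might try to count how many of the IOP comparisons a single error would alter. SAP section 5 groups by subject, not by bottle or visit, and SAP section 7.4 does not say whether the ANCOVA is fitted to two arms or four. No firm count follows.
- A reader might infer that subjects who miss doses or stop early would be moved to vehicle. Nothing in the rule says so.

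**Conclusion.** The point holds as a matter of text: the ITT comparison of IOP with vehicle is as-treated as written. Its effect is nil unless a subject receives a treatment other than the one assigned. The documents report no such error and give no rate, and no bias is demonstrated. The change is worth making because a grouping rule matters only when an error happens, and it is credible only if fixed before the code is broken.

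The power figures assume whole-course errors in one active arm, vehicle-like response in those subjects, and 20 analysed subjects per arm. The numbers of errors are hypothetical.

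There is also a secondary gap. Bottles are supplied separately, since "the second IP bottle will be dispensed to the subject on Day 14" and a third is held in reserve. A subject could therefore receive more than one treatment, and the SAP does not say which would count as actual. This is a detail to clarify, not a second fault of the same weight.

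**What to change.** Replace the last sentence of SAP section 5 with: *ITT efficacy analyses, and disposition and baseline tables, are by randomised treatment; Safety Population analyses are by treatment actually received.* Including the disposition and baseline tables also places any subject who was randomised but never dosed, who has no actual treatment. Name the Per Protocol grouping in the same place, because removing the blanket sentence would otherwise leave it unstated. An as-treated IOP analysis may be kept as a sensitivity analysis.

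As a secondary clarification, state before unmasking how a subject who received more than one treatment is grouped in the safety analyses.

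The cost is one replaced sentence and one short handling rule, with no change to data collection or sample size. The downside arises only if errors occur: as-randomised power would then be roughly 3 points lower with one active-arm subject on vehicle throughout, and roughly 7 points lower with two.

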6. HANDLING OF MISSING DATA

Missing data will not be imputed for efficacy assessments.

If intensity of an adverse event is missing the event will be considered severe. If relationship of adverse event to study drug is missing the event will be counted as related.

Adverse events will be considered treatment emergent unless it can be determined from the onset or end date information that the event cannot have been treatment emergent.

Other adverse events will be assumed to occur during the screening period.

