4.3 Subject Withdrawal and/or Discontinuation

Subjects are free to discontinue their participation in the study at any time without prejudice to further treatment. The investigator must withdraw any subject from the study at their request. Subjects should provide the reason for withdrawal and confirm whether they are withdrawing consent or withdrawing from IP treatment and will continue to participate in the study. The investigator or Allysta Pharmaceuticals, Inc., may withdraw the subject from IP treatment for any reason or if the subject meets any of the following criteria.

- Experiences a serious or intolerable AE that is judged by the investigator to preclude further study participation.
- Develops a clinically significant laboratory or other abnormality that is judged by the investigator to be potentially related to IP.
- Requires a medication that is prohibited by the protocol. Contact the Medical Monitor to discuss exiting a subject due to use of a prohibited medication before exiting the subject.
- Does not follow the protocol procedures, including noncompliance.
- Is lost to follow-up; every effort should be made to contact the subject.
- Administrative reasons, including termination of the trial by the Sponsor, unavailable for follow-up procedures.

- Experiences glaucomatous progression and/or unacceptable IOP elevation, per the discretion of the investigator.

Should a subject's medical or mental condition change or become unstable during the study, such that the ability of the subject to continue in this study becomes compromised or, in the investigator's judgment, their health is jeopardized, or further continuation is unadvisable, the subject may be withdrawn from study treatment and/or withdrawn from the study.

If a subject prematurely withdraws from the study, either at her/his request or at the discretion of the investigator or Allysta Pharmaceuticals, Inc. the reason for withdrawal should be recorded. All subjects prematurely discontinuing study dosing, regardless of cause, will return within 14 days from their last dose of IP to complete Early Termination visit assessments; consult the Medical Monitor to determine which diurnal measurements, if any, are required for the ET visit. Study subjects who withdraw from the study may be replaced at the Sponsor's discretion.

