8.4 Significance

For superiority testing, a 2-sided test with a significance level of $p \leq 0.05$ will be used.

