2.3 Study Design/ Procedures

The study will evaluate the safety, tolerability, and preliminary efficacy of 3 concentrations of H-1337 and vehicle administered twice daily for 28 days. Up to 100 subjects, naïve to H-1337, will be randomized and dosed for 28 days. The parallel group, double-masked, placebo-controlled study will include the following dosing cohorts:

H-1337 0.06% (n=20)

H-1337 0.2% (n = 20)

H-1337 0.6% (n = 20)

Control (Vehicle) (n = 20)

Dosing will be BID unilaterally in the study eye for the first 3 days, then BID OU from Day 4 to Day 28.

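### Separate complete-case ANCOVAs can pull the Day 28 difference toward zero if more vehicle than active subjects leave for high IOP; a joint repeated-measures model would reduce this without imputation

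*SAP*

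**What the plan says.** SAP 7.4 compares each H-1337 arm with vehicle on IOP, diurnal IOP and their changes, "compared to the placebo group using the analysis of covariance (ANCOVA) model, separately for each time point", with the baseline value as covariate. SAP 6 adds "Missing data will not be imputed for efficacy assessments", and Protocol 8.5 says the same, on the grounds that the trial is small, brief and exploratory and that missing data should be few. Neither document plans a repeated-measures model or a missing-data sensitivity analysis for efficacy.

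IOP-related loss is foreseen. Protocol 4.3 lists this among the withdrawal criteria: "Experiences glaucomatous progression and/or unacceptable IOP elevation, per the discretion of the investigator". Protocol 4.4 allows withdrawal from study treatment and the start of other IOP treatment, and SAP 7.1 has a discontinuation category for uncontrolled IOP.

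Protocol 4.3 also provides an early termination visit within 14 days of the last dose. Which diurnal readings are taken there, if any, is settled with the Medical Monitor. The schedule puts this visit in the same column as Day 28. The SAP does not say whether its readings count as Day 28 values.

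**The concern.** Each ANCOVA uses only the subjects measured at that visit and time. Subjects are off all other IOP-lowering drugs for the whole study and enter at 23 to 32 mmHg. If H-1337 works, those who leave for high IOP should come mostly from vehicle. Their absence at Day 28 removes the upper end of the vehicle distribution and flatters vehicle.

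Change from baseline at Days 14 and 28 is the primary efficacy measure (Protocol 6.1), and the sample size is driven by the IOP effect. One vehicle arm serves all three comparisons, so a selected vehicle arm would shift all three in the same direction. For a subject who leaves after Day 14, the Day 14 reading predicts the missing Day 28 value, but the planned analysis does not use it.

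**Working it through.** **1. The plan's own figure.** SAP 4: "this protocol is powered at 94% to detect a difference in IOP reduction of 4.0 mmHg" "against a standard deviation of 3.5 mmHg", with 20 per group and two-sided alpha 0.05. Standard error = 3.5 × √(2/20) = 1.107. Noncentrality = 4.0/1.107 = 3.61 on 38 df. Power = 0.941, so the stated 94% reproduces. It makes no allowance for loss.

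**2. Closed form for the attenuation.** Assumptions not in the documents: the effect is 4.0 at each visit, both arms have the same SD, the correlation ρ between Day 14 and Day 28 is 0.5 to 0.7, and subjects leave after Day 14 when their Day 14 IOP is high. If a fraction p of an arm is lost from the top, the mean Day 14 change of those who stay falls by SD × φ(z)/(1 − p), where z is the upper p-quantile of the standard normal and φ its density. The Day 28 mean falls by ρ times that. Ignoring baseline spread:

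attenuation = ρ × 3.5 × [φ(z_V)/(1 − p_V) − φ(z_A)/(1 − p_A)]

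- Losses 3.7% vehicle, 0.3% active: 3.5 × 0.0809/0.963 = 0.294; 3.5 × 0.0091/0.997 = 0.032; difference 0.26; times ρ = 0.13 to 0.18.
- Losses 9.6% and 1.2%: 3.5 × 0.1703/0.904 = 0.659; 3.5 × 0.0312/0.988 = 0.111; difference 0.55; times ρ = 0.27 to 0.38.
- Losses 20.6% and 3.7%: 3.5 × 0.2849/0.794 = 1.256; 3.5 × 0.0809/0.963 = 0.294; difference 0.96; times ρ = 0.48 to 0.67.

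**3. Simulation with baseline IOP as covariate.** 300,000 subjects per arm, vehicle change −1 mmHg. Loss was varied by cut-offs of 32, 30 and 28 mmHg. These are simulation devices only, since the documents give no threshold. Day 28 effect in mmHg, true value 4.0:

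| Vehicle / active loss | Complete-case ANCOVA, ρ = 0.5 / 0.7 | Repeated-measures model, ρ = 0.5 / 0.7 |
|---|---|---|
| 3.7% / 0.3% | 3.90 / 3.83 | 4.01 / 3.99 |
| 9.6% / 1.2% | 3.74 / 3.66 | 3.98 / 4.00 |
| 20.6% / 3.7% | 3.55 / 3.37 | 4.00 / 4.00 |

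A separate run at vehicle losses of 4%, 11% and 23% gave complete-case effects of 3.83–3.86, 3.60–3.73 and 3.32–3.50.

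**4. Where the bias vanishes.** With no drug effect, the estimate stays at zero. With 15% loss unrelated to IOP in both arms, it stays at 4.01. If half the active subjects respond by 8 mmHg and half not at all, complete-case ANCOVA gives 3.97–3.98 and the repeated-measures model overshoots slightly, at 4.01–4.09.

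**5. Trial-size effect (20 per arm, ρ = 0.7).** At about 10% vehicle loss, the mean complete-case estimate is 3.66 and power falls from 0.93 to 0.88. At about 21%, they are 3.39 and 0.81. The repeated-measures estimate stays at about 4.0, with an SD of 1.15 to 1.18 against 1.13 with full data.

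**6. Limits of the remedy** (ranges over ρ = 0.5 to 0.8).
- Withdrawal follows an unrecorded IOP: the model returns 3.84–3.99, so some bias remains.
- Withdrawal starts from Day 4, but the model holds only Days 14 and 28: it returns 3.33–3.91, against 3.09–3.83 for complete cases. With Day 4 in the model it returns about 4.0.

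The second limit matters here. SAP Appendix 2 has only T0 readings at Days 1 and 4. A model fitted clock time by clock time would hold no post-baseline value, at five of the six times, for anyone who left before Day 14.

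**The case against.** Protocol 8.5 expects few missing data. Entrants have completed any washout, had IOP no higher than 32 mmHg at all time points, and were excluded if glaucoma made stopping treatment unsafe. No IOP withdrawals at all is plausible. With 20 vehicle subjects, 4%, 10% and 20% are 0.8, 2 and 4 people, and the attenuation is below the 1.11 mmHg standard error of the comparison. It works against the drug, so it does not create a false claim of efficacy. Loss after Day 14 leaves the Day 14 contrasts intact. Withdrawals on active for hyperemia could even out the loss between arms. Efficacy is a secondary objective, and SAP 7.1 tabulates discontinuation reasons by arm, so imbalance would be visible.

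All of this stands, and it limits the point to a conditional one. It does not remove it: the expectation of few missing data carries no figure, a visible imbalance is not a corrected estimate, and the better model costs almost no precision.

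A reader might also infer that withdrawn subjects simply have no later data. The documents do not settle this. Early termination IOP may be collected, and Protocol 4.3 lets a subject stop study drug and stay in the study. The gap is that no rule says how such readings are used.

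**Conclusion.** The planned analysis can bias the Day 28 difference toward zero, by about 0.1 to 0.2 mmHg at 4% vehicle loss, 0.3 to 0.4 at about 10% and 0.5 to 0.7 at about 20%. This rests on a true effect of 4.0 mmHg, SD 3.5 in both arms, visit correlation 0.5 to 0.7, and loss that is driven by high Day 14 IOP and heavier on vehicle.

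Two stronger readings are not supported. One is that the Day 28 result is biased as planned: the documents give neither a withdrawal rate nor an IOP threshold, and the bias is nil if the drug has no effect or dropout is unrelated to IOP. The other is that any repeated-measures model removes the problem: that holds only if withdrawal depends on recorded IOPs that are in the model. This is a cheap improvement, not a flaw that invalidates the plan.

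**What to change.** Before database lock, amend SAP 6 and 7.4 as follows.

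- Analyse change in IOP with a mixed model for repeated measures on observed values, using all scheduled post-baseline readings. Include treatment, visit/time, their interaction, time-matched baseline and randomisation stratum. Report the Day 14 and Day 28 contrasts.
- Model clock times jointly, or at least put the Day 1 and Day 4 T0 readings into the models for later clock times. Under the SAP schedule, the full joint version has 1 + 1 + 6 + 6 = 14 readings, and an unstructured covariance has 14 × 15/2 = 105 parameters for about 80 subjects. The smaller version has four readings and 4 × 5/2 = 10 parameters. Prespecify which is used.
- Keep the by-time-point ANCOVA as a sensitivity analysis.
- State that early termination readings, and readings after new IOP treatment, are not entered as ordinary Day 28 on-treatment values.
- Reconcile the Day 4 IOP times: six in the protocol schedule, T0 only in SAP Appendices 1 and 2. This decides what the model can use for early leavers.

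The cost is SAP text and modest programming, and the no-imputation rule is respected. The downside is reliance on missing at random given recorded IOPs. A sensitivity analysis that departs from that assumption would show how much rests on it.
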